9.2. Screening and Eligibility Assessment

The screening and eligibility assessment will involve two stages:

Stage 1: Identified potential participants will be invited to complete a screening questionnaire to appraise key inclusion/exclusion criteria. The screening questionnaire will be presented to potential participants via their preferred method of communication, or a hybrid of preferred methods as outlined in Section 9.1. Potential participants will be asked to consent to completing the screening questionnaire, which at the end will ask participants (if eligible) to provide identifying information (full name, email address, phone number, name of GP surgery) in order to schedule stage 2. We will also ask participants how they found out about the trial for more effective monitoring of trial recruitment strategies. This information will be reviewed by the trial management group (TMG) regularly during the trial to inform and guide recruitment approaches.

The screening questionnaire comprises the following items and measures to assess key inclusion/exclusion criteria at stage 1, which are shown in Table 5, below:

Inclusion Criterion	Assessed by
GP Practice	List of GP practices open to study
Age	Reported age
Depressive symptoms	PHQ9 (>=10)
Insomnia symptoms	SCI
Sleep efficiency <85%	PSQI items 1+3 [difference score=TIB]/PSQI item 4 [TST]*100
Exclusion Criterion	
Pregnant/pregnancy planning, diagnosis of sleep disorder, dementia or MCI, epilepsy, schizophrenia or bipolar disorder, currently or recently received in-patient psychiatric treatment, cancer treatment or planned major surgery during treatment phase, life expectancy <1 year, currently receiving psychological treatment for insomnia or online treatment programme, previously received sleep restriction therapy,	Yes/No response
• •	Bespoke questionnaire item

Stage 2: For those meeting the above criteria a brief interview will be arranged with a trained member of the research team. The interview will take place over the phone, online, or in-person at the participating GP surgery, to further ascertain study eligibility. We will also ask whether the participant has access to a computer or tablet and an internet connection at home for operational purposes.

The interview at stage 2 will appraise the following inclusion/exclusion criteria, which are shown in table 6, below:

Table 6: Inclusion/exclusion	criteria at stage 2 of screening
------------------------------	----------------------------------

Inclusion Criterion	Assessed by
Major depressive episode	SCID-5 (13)
Insomnia disorder	Bespoke questions mapping onto DSM-5 diagnostic criteria
Exclusion Criterion	
Recent history of suicide attempt and current suicidal ideation and intent	C-SSRS (14)
Substance use dependence over the past 12 months	SISQ (15) and SCID-5 (13)
Alcohol dependence	AUDIT (16) (>=14 Female/>=16 Male) and clinical judgement
Additional sleep disorder symptoms	Sleep Disorders Screen administered as semi-structured interview (40)
Taking part in additional clinical trial	Bespoke item
Another member of household taking part	Yes/No

Clinical Research Protocol Template version 15.0

© Copyright: The University of Oxford and Oxford University Hospitals NHS Foundation Trust 2019 Page 23 of 52 A baseline visit will be scheduled for all potential participants meeting all eligibility criteria (within 4 weeks of eligibility assessment) where they will complete baseline questionnaires, tasks from the Oxford Emotional Test Battery, and be provided with a sleep diary and actigraph watch to wear for the next 7 days.

Rescreening: If it is not possible to arrange a participant baseline within 4 weeks of the clinical interview section of the eligibility assessment, participants will be rescreened to ensure they are still eligible before the baseline assessment takes place. Rescreening may either take place prior to or at the baseline visit, whichever is more convenient for the participant. Re-screening for stage 1 will also take place if the time between stage 1 and stage 2 is more than 8 weeks.

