4. ABBREVIATIONS

Table 3: Table of abbreviations

AE	Adverse event
AR	Adverse reaction
BADS-SF	Behavioural Activation for Depression Scale (Short form)
BC-CCI	British Columbia Cognitive Complaints Inventory
BDI	Beck Depression Inventory
CACE	Compiler Average Causal Effect
CI	Chief Investigator
CSRI	Client Service Receipt Inventory
CRF	Case Report Form
CSD	Consensus Sleep Diary
DMC	Data Monitoring Committee
DMP	Data Management Plan
ECAT	Emotional Categorisation Task
EMEM	Emotion
FERT	Facial Expression Recognition Task
GCP	Good Clinical Practice
GP	General Practitioner
HRA	Health Research Authority
ICF	Informed Consent Form
IRB	Independent Review Board
IS	Interdaily Stability
ISI	Insomnia Severity Index
NIHR:EME	National Institute for Health and Care Research: Efficacy and Mechanism Evaluation Programme
NHS	National Health Service
PANAS	Positive and Negative Affect Schedule

Clinical Research Protocol Template version 15.0

© Copyright: The University of Oxford and Oxford University Hospitals NHS Foundation Trust 2019

PC-CTU	Primary Care Clinical Trials Unit
PHQ-9	Patient Health Questionnaire-9
PSQI	Pittsburgh Sleep Quality Index
RCT	Randomised Controlled Trial
PTQ	Perseverative Thinking Questionnaire
PI	Principal Investigator
PIS	Patient Information Sheet
R&D	NHS Trust R&D Department
RA	Relative Amplitude
REC	Research Ethics Committee
RGEA	Research Governance, Ethics and Assurance team
RSI	Reference Safety Information
SAE	Serious Adverse Event
SAP	Statistical Analysis Plan
SAR	Serious Adverse Reaction
SCID-5	Structured Clinical Interview for DSM-5
SDV	Source Data Verification
SE	Sleep Efficiency
SISQ	Single-Item Screening Question [for substance use]
SOL	Sleep Onset Latency
SOP	Standard Operating Procedure
SRT	Sleep Restriction Therapy
SUSAR	Suspected Unexpected Serious Adverse Reactions
TAU	Treatment As Usual
TIB	Time in bed
TIDieR	Template for Intervention Description and Replication checklist
TMF	Trial Master File

Clinical Research Protocol Template version 15.0

© Copyright: The University of Oxford and Oxford University Hospitals NHS Foundation Trust 2019

TSC	Trial Steering Committee
TST	Total Sleep Time
WASO	Wake After Sleep Onset
WEMWBS	Warwick-Edinburgh Mental Wellbeing Scale

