8.2. Inclusion Criteria

- Participant is willing and able to give informed consent for participation in the trial.
- Aged 18 years or above.
- Screen positive for depressive symptoms on the PHQ-9 (≥10) and meet criteria for major depressive disorder, assessed via the Structured Clinical Interview for DSM-5 (SCID-5)
- Screen positive for insomnia symptoms on the sleep condition indicator and meet criteria for insomnia disorder
- Self-reported sleep efficiency <85% over the past month, assessed via the Pittsburgh Sleep Quality Index (PSQI)
- Able to attend appointments for assessments and treatment and adhere to study procedures
- The participant's GP surgery is participating in the trial

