24. APPENDIX C: AMENDMENT HISTORY

Table 12: Table of Amendments

Amendment No.	Protocol Version No.	Date issued	Author(s) of changes	Details of Changes made
1	3.0	03 April 2023	[name], [name], [name]	Update to sample size and allocation ratio as a result of need to account for therapist effect. Update to Stop/Go criteria at the request of the funder. Minor wording changes throughout the document for clarity, consistency and ease of reading.
2	4.0		[name]	Update to eligibility assessments and recruitment strategies; minor wording changes throughout the document for clarity

25. APPENDIX D: TIDieR Checklist for Intervention Description and Replication

Name of intervention	Sleep Restriction Therapy (SRT) for Insomnia Disorder
Why	Insomnia is assumed to be maintained, in part, by excessive amounts of time in bed and irregular sleep-wake schedules, which serve to fragment sleep. Time in bed awake further contributes to insomnia because the bed/bedroom environment may become associated with wakefulness over time; subsequently acting as a trigger for arousal and sleep fragmentation. SRT aims to: 1) restrict time in bed [to enhance sleep efficiency]; 2) regularise the timing of the sleep-wake cycle; and 3) recondition the bed-sleep association.
What: Materials	Materials for patients : patients will be provided with a folder at the beginning of the intervention. This folder contains: a copy of the slides used during session 1; worksheets to complete during sessions 1-6; sleep diaries and sleep efficiency grids to enable recording of sleep efficiency each day during the 6week intervention period; and a booklet which contains enhanced information on the background and implementation of SRT, including quotes from patients who have previously underwent SRT

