L					

Tailoring		The treatment will be tailored to each individual's sleep pattern but follows standardised instructions for setting and titrating time in bed (TIB):				
	Criterion	SRT				
	Calculation of prescribed time in bed (TIB)	Based on average total sleep time (TST) from 7-day sleep diary. Minimum TIB = 5 hrs.				
	Rise time selection	Time that aligns with working schedule and can be adhered to 7 days a week				
	Bedtime selection	Typically delayed in order to equal the prescribed TIB.				
	Weekly adjustments to TIB based on average sleep efficiency for 7	 a) SE ≥ 85% increase TIB by 15 minutes b) SE = 80-84% no change to TIB c) SE ≤ 79% decrease TIB by 15 minutes 				
	days (SE) (sessions 26)	Adjustments (advancing or delaying) are typically made to the prescribed bedtime.				
	Napping	Recommendation to eliminate all napping				
	circumstances: patient patient is excessive implementation. In th revised time in bed (in	Nurses will be encouraged to adapt the TIB prescription in the following circumstances: patient is struggling to adhere or cannot tolerate the restriction; patient is excessively sleepy; or change in health precludes full implementation. In these circumstances nurses will be encouraged to agree a revised time in bed (increasing in 15 minute blocks) until the patient is content. On completion of nurse sessions, participants are encouraged to continue self				
	implementing SRT on their own according to the standardised rules. Participants are provided with sleep diaries and grids to enable self implementation at home. Once daytime functioning has improved and sleep efficiency remains high – and no further sleep is obtained with additional TIB – the participant is considered to have reached their optimal sleep schedule.					
How well	appraised for fidelity behavioural therapy for checklist at the end of	Sessions are audio-recorded (if consent is provided) and independently appraised for fidelity by a Clinical Psychologist experienced in cognitive behavioural therapy for insomnia. Nurses will follow and 'sign-off' a checklist at the end of each session in order to capture duration of session and adherence to treatment instructions.				

26. APPENDIX E: Examples of the FERT and ECAT Measures

Facial Expression Recognition Task (FERT) via P1vital Products Ltd. ePRO system

Example task instructions shown to participant

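### Table 5 inverts the sleep-efficiency formula, so no consistent respondent can meet the <85% inclusion criterion as written

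*Protocol*

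**What the plan says.** Section 8.2 of the Protocol lists as an inclusion criterion "Self-reported sleep efficiency <85% over the past month, assessed via the Pittsburgh Sleep Quality Index (PSQI"). It gives no formula there.

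Table 5 in section 9.2 sets out how each criterion is assessed at stage 1. Beside "Sleep efficiency <85"% it gives "PSQI items 1+3 [difference score=TIB]/PSQI item 4 [TST]*100". The abbreviations in section 4 confirm the labels: "TIB Time in bed" and "TST Total Sleep Time". The numerator is therefore time in bed and the denominator total sleep time. No other section gives a screening formula or corrects this one.

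Stage 1 decides who goes on to stage 2: "For those meeting the above criteria a brief interview will be arranged with a trained member of the research team".

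Appendix D (the TIDieR description of the intervention) also uses sleep efficiency. One stated aim of SRT is to "restrict time in bed [to enhance sleep efficiency"], and the weekly adjustment rules include the band "SE = 80-84% no change to TIB", with further bands at 85% and above and at 79% and below.

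**The concern.** Sleep efficiency is the percentage of time in bed that is spent asleep. Table 5 prints the reciprocal and pairs it with a cut-off that suits the proper ratio. Sleep takes place within time in bed, so the printed quantity has a floor of 100%, and a threshold of <85% lies wholly outside its range.

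This is the only stated calculation for an inclusion criterion, and it applies to everyone who is screened. Under section 9.1 screening can be done online, through a link on a phone, on paper followed by a call, or directly with a researcher. Under section 9.2 the questionnaire asks for contact details only from people found eligible. If the printed formula were coded into the form, consistent respondents would be turned away before the team could reach them, and only people giving contradictory sleep times would get through. The same calculation would recur whenever stage 1 is repeated because more than 8 weeks have passed before stage 2.

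If staff read past the slip and divide the right way round, the intended people are screened in, but eligibility cannot be audited against the calculation in the approved text.

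**Working it through.** **Inputs**
- Printed formula: TIB / TST x 100 (Table 5, section 9.2).
- Cut-off: <85% (Table 5 and section 8.2).
- TIB is time in bed and TST is total sleep time (section 4).
- Constraint: 0 < TST ≤ TIB for internally consistent answers.

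**Range of the printed formula.** From TST ≤ TIB it follows that TIB / TST ≥ 1, so TIB / TST x 100 ≥ 100. The minimum, 100%, occurs when the whole time in bed is spent asleep.

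**What a pass would require.** TIB / TST < 0.85 means TST > TIB / 0.85 = 1.176 x TIB. With 8 h in bed, reported sleep would have to exceed 8 / 0.85 = 9.41 h. The proper efficiency would then be above 100 / 0.85 = 117.6%, which is impossible.

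**Examples with 8 h in bed**

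| TST (h) | As printed, TIB / TST x 100 | TST / TIB x 100 | Meets <85% as printed | Meets <85% with TST / TIB |
|---|---|---|---|---|
| 5 | 160.0% | 62.5% | no | yes |
| 6 | 133.3% | 75.0% | no | yes |
| 6.8 | 117.6% | 85.0% | no | no (at the cut-off) |
| 7 | 114.3% | 87.5% | no | no |
| 8 | 100.0% | 100.0% | no | no |

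The first two rows are people the trial means to recruit, and the printed rule excludes both.

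**Wider check.** I took TIB from 4 to 12 h and TST from 1 h up to TIB, in 15-minute steps (an assumed range, 957 combinations). As printed, 0 of 957 fall below 85% and the minimum is 100.0%. With TST / TIB, 781 of 957 fall below 85%. The grid only illustrates the algebra; 781 of 957 is not an estimate of how many people would be eligible.

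**Which direction the protocol intends.** Appendix D says that restricting time in bed should raise efficiency. Hold TST at 5.5 h and shorten TIB from 8 h to 7.75 h:
- as printed: 8 / 5.5 = 145.5% falls to 7.75 / 5.5 = 140.9%;
- TST / TIB: 5.5 / 8 = 68.8% rises to 5.5 / 7.75 = 71.0%.

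Only the second moves as Appendix D describes. The two lower bands there (80-84%, and 79% or less) could never occur with the printed ratio.

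**The case against.** The strongest reply is that this is a slip in shorthand, not a rule anyone would follow. Section 8.2 states the criterion itself correctly, and Table 5 merely says which questionnaire items feed it. The cell is plainly informal: it joins items 1 and 3 with a plus sign and then calls the result a difference, so a programmer has to interpret it anyway. The error would also expose itself. Had it been coded as printed, almost nobody would pass stage 1, and section 9.11 has recruitment reviewed monthly against a target of 63 participants in four months. The synopsis plans recruitment from December 2022 and Appendix C lists an amendment of April 2023 and a later one, which makes a total block on screening unlikely to have persisted, although the protocol does not report actual enrolment. Finally, the sample size, primary outcome and analysis model are untouched.

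Much of this stands. A notation error is more likely than silent mis-selection, and the treatment comparison is not biased by it. Anyone using TST / TIB would be applying section 8.2 in the sense the protocol uses elsewhere. But the bracketed labels, the slash and the multiplication by 100 leave no reading other than a ratio, and section 8.2 gives no formula that could override it. The only written instruction for calculating this criterion still returns the wrong answer for everyone who should qualify.

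**Conclusion.** The formula is wrong as written. With consistent answers it can never return less than 100%, so the <85% criterion in section 8.2 cannot be satisfied by following Table 5. The conclusion rests on one assumption, that reported sleep does not exceed reported time in bed; it needs no outside source, and Appendix D settles the intended direction.

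The practical effect depends on something the protocol does not show, namely how the screening form and any manual scoring were set up. If they use TST / TIB, nobody was wrongly screened and only the document is at fault. If they use the printed ratio, every consistent respondent would fail stage 1. It should be corrected in either case, because it governs entry to the trial.

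**What to change.** In Table 5, replace the entry with: PSQI item 4 [TST] / time elapsed between PSQI items 1 and 3 [TIB] x 100. Writing the denominator as an elapsed time also removes the confusing plus sign. Leave the 85% cut-off as it is.

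Then confirm that the online form and any manual scoring by researchers use this direction, and record that confirmation. If any route used the printed ratio, recalculate sleep efficiency for the people screened by that route and re-check their eligibility.

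The cost is a one-line protocol correction and one check of the form's code and scoring instructions. The sample size and the analysis need no change.

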9.3. Informed Consent

The participant will receive the PIS detailing no less than: the exact nature of the trial; and the known side effects and risks involved in taking part. It will be clear that the participant is free to withdraw from the trial at any time, without the need to provide a reason and in knowledge of the fact that withdrawing from the trial will not affect their future care from their healthcare provider. Adequate time will be given to the participant to consider the information and to ask any questions about the trial before deciding whether to participate. Written or remote informed consent will then be obtained by means of a conversation between the participant and researcher at the baseline visit by means of participant dated signature and dated signature of the person who presented and obtained the informed consent, or in the case of remote informed consent, dated signature of the person who witnessed and obtained the informed consent. Written informed consent or informed e-consent will be obtained in instances where the participant and the person obtaining consent are meeting face-to-face; informed e-consent will be obtained in instances where this meeting is not conducted face-to-face (i.e. remotely). The type of consent form used will be at the discretion of whether the participant chooses an in-person meeting or online meeting for the baseline visit. The person who obtains consent will be qualified and experienced and be authorised to do so by the chief investigator (CI). A copy of the signed informed consent will be given to the participant; a copy will be retained in the medical notes and the third copy in the investigator site file. Where a paper consent form is used, the participant must personally sign and date the latest approved version of the Informed Consent Form (ICF) or the researcher must sign and date the latest approved version of remote ICF before any study specific procedures are performed. Where electronic consent is used, the participant will complete the electronic consent form themselves, and a copy will be emailed to the participant.

9.4. Randomisation

Following baseline assessments, participants will be eligible for randomisation. Eligible participants will be randomised to SRT+TAU (135 participants) or TAU (115 participants) using a secure, validated and compliant web-based randomisation system (Sortiton), with a non-deterministic minimisation algorithm to ensure practice, use of antidepressant medication (yes/no), current receipt of psychological therapy for depression (yes/no), age (18-65yrs vs. >65yrs), sex (male/female/other), baseline insomnia severity (ISI score: <22 vs. 22-28) and depression severity (PHQ-9 score: <19 vs. 19-27) are balanced across the two groups. Individual randomisation is appropriate because the risk of control group contamination is very low: treatment will be delivered by trained research nurses who will be independent from the practice and will only interact with participants in the experimental arm.

9.5. Blinding and codebreaking

The study is an open label trial. The participants and nurses will know the treatment allocation due to the design of the study. Treatment providers (i.e. nurses delivering SRT) will not be involved in the collection of trial outcomes. Outcomes (questionnaires, actigraphy, computer tasks) will be self-completed, limiting the possibility of observer/interviewer bias. Communication from the research team to participants, post-randomisation, will be limited to collection of outcome assessments and not therapeutic procedures. Should participants want to complete questionnaire outcomes over the phone, we will ensure that the researcher is blind to group allocation. Actigraphy data will be scored by a researcher who will be blind to group allocation.

9.6. Description of study intervention(s), comparators and study procedures (clinical)

9.6.1. Description of study intervention (SRT+TAU)

Participants randomised to the intervention arm will be offered nurse-delivered insomnia therapy in the form of sleep restriction therapy (SRT), a manualised behavioural intervention (see Appendix D for detailed description of the intervention included as a TIDieR checklist (Template for Intervention Description and Replication [ref]). SRT will be in addition to TAU. SRT will be delivered by trained nurses over six brief weekly sessions and participants in the intervention arm will receive a booklet at the first session. The six sessions will comprise three in-person sessions (1/3/5) and three remote sessions (2/4/6), although all sessions could be delivered remotely if needed (e.g., due to participant preference, scheduling difficulties, COVID restrictions, or room availability at practice).

Nurses will complete an "intervention checklist" at the end of each session, to 'sign off' coverage of key treatment ingredients and indicate start/end times to ensure standardisation of dose. To enable fidelity assessment, SRT sessions will be audio recorded, if participants provide informed consent at baseline. A sample of these will then be rated by a member of the research team.

To permit quantification of patient adherence to SRT guidance, sleep diaries completed during the intervention phase will be returned to the research team.

Nurse training of SRT and supervision: Suitably experienced members of the team will deliver manualised training to research nurses, covering sleep and insomnia, depression, the interaction between sleep and depression, and SRT. The team has an extensive track record of delivering SRT training in the context of trial evaluation but also to a range of health professionals through educational programmes (e.g., Oxford Online Programme in Sleep Medicine, Doctorate in Clinical Psychology), workshops, books and CPD events. Training will involve a 2-day workshop consisting of informational delivery and structured review and discussion of example clinical vignettes. All nurses will be trained to adhere to a manual and will be provided with a list of FAQs to enable troubleshooting of potential issues that may arise during patient consultations.

